6.3.2. PD Endpoints

None.

6.4. Covariates

None.

7. HANDLING OF MISSING VALUES

For the analysis of safety endpoints, the sponsor data standard rules for imputation will be applied.

7.1. Concentrations Below the Limit of Quantification

In all data presentations (except listings), concentrations below the limit of quantification (BLQ) will be set to zero. (In listings BLQ values will be reported as “<LLQ”, where LLQ will be replaced with the value for the lower limit of quantification).

7.2. Deviations, Missing Concentrations and Anomalous Values

In summary tables and plots of median profiles, statistics will be calculated having set concentrations to missing if 1 of the following cases is true:

1. A concentration has been collected as ND (ie, not done) or NS (ie, no sample);
2. A deviation in sampling time is of sufficient concern or a concentration has been flagged anomalous by the pharmacokineticist.

Note that summary statistics will not be presented at a particular time point if more than 50% of the data are missing.

7.3. Pharmacokinetic Parameters

Actual PK sampling times will be used in the derivation of PK parameters.

If a PK parameter cannot be derived from a subject's concentration data, the parameter will be coded as NC (ie, not calculated). (Note that NC values will not be generated beyond the day that a subject discontinues).

In summary tables, statistics will be calculated by setting NC values to missing; and statistics will be presented for a particular treatment with ≥ 3 evaluable measurements. For statistical analyses (ie, analysis of variance), PK parameters coded as NC will also be set to missing; and analyses will not be performed for a particular parameter if more than 50% of the data are NC.

If an individual participant has a known cause for biased estimate of a PK parameter (due, for example, to an event such as vomiting before all of the drug is absorbed in the body), this will be footnoted in summary tables and will not be included in the calculations of summary statistics or statistical analyses. Participants who vomit at or before 2 times of median T_{max} after drug administration may be excluded from PK analyses.

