9.3. Statistical Analyses

The SAP will be developed and finalized prior to database lock before any analyses are performed and will describe the analyses and procedures for accounting for missing, unused, and spurious data. This section is a summary of the planned statistical analyses of the primary and secondary endpoints

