9.3.1. Pharmacokinetics Endpoint(s)

Bosutinib PK parameters following a single dose administration will be estimated from the concentration time profiles using non-compartmental methods as data permit. The various PK parameters to be assessed in this study, their definition, and method of determination are outlined in Table 5. In all cases, actual PK sampling times will be used in the derivation of PK parameters.

Table 5. Definitions of PK Parameters

Parameter	Definition	Method of Determination
AUC _{last}	Area under the plasma concentration time profile from time zero to the time of the last quantifiable concentration (C _{last})	Linear-log trapezoidal method
AUC _{inf} ^a	Area under the plasma concentration-time profile from time zero extrapolated to infinite time	AUC _{last} + (C _{last} */k _{el}) where C _{last} * is the predicted plasma concentration at the last quantifiable time

Table 5. Definitions of PK Parameters

Parameter	Definition	Method of Determination
		point estimated from the log-linear regression analysis and k_{el} is the terminal phase rate constant calculated by a linear regression through at least 3 data points in the terminal phase of the log-linear concentration-time curve.
C_{max}	Maximum plasma concentration	Observed directly from the data
T_{max}	Time for C_{max}	Observed directly from the data as time of first occurrence
$t_{1/2}^a$	Terminal elimination half-life	$\text{Log}_e(2)/k_{el}$ Only those data points judged to describe the terminal log-linear decline will be used in the regression.
CL/F^a	Apparent clearance after oral dose	$\text{Dose}/\text{AUC}_{inf}$ after oral dose
V_z/F^a	Apparent volume of distribution after oral dose	$\text{Dose}/(\text{AUC}_{inf} \cdot k_{el})$ after oral dose

a. As data permits.

Natural logarithm-transformed AUC_{inf} , AUC_{last} and C_{max} will be analyzed using a mixed effect model with sequence, period and treatment as fixed effects and participant within sequence as a random effect. Estimates of the adjusted mean differences (Test-Reference) and corresponding 90% CIs will be obtained from the model. The adjusted mean differences and 90% CIs for the differences will be exponentiated to provide estimates of the ratio of adjusted geometric means (Test/Reference) and 90% CIs for the ratios.

The following 2 comparisons will be performed:

- Treatment A (Test) vs Treatment C (Reference)
- Treatment B (Test) vs Treatment C (Reference)

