The plasma PK parameters AUC_{inf} , C_{max} , AUC_{last} , T_{max} , CL/F , V_z/F and $t_{1/2}$ of bosutinib will be summarized descriptively by treatment. For AUC_{inf} , AUC_{last} and C_{max} , a listing of the individual participant ratios (Test-Reference) will be provided for the 2 comparisons described above. Individual participant PK parameters for AUC_{inf} , AUC_{last} and C_{max} will be plotted by treatment and overlaid with geometric mean. Concentrations will be listed and summarized descriptively by PK sampling time and treatment. Individual participant and median profiles of the concentration-time data will be plotted by treatment. For summary statistics and median plots by sampling time, the nominal PK sampling time will be used, for individual participant plots by time, the actual PK sampling time will be used.

If an individual participant has a known cause for biased estimate of a PK parameter (due, for example, to an event such as vomiting before all of the drug is absorbed in the body), this will be footnoted in summary tables and will not be included in the calculation of summary

statistics or statistical analyses. Participants who vomit at or before 2 times of median T_{max} after drug administration may be excluded from PK analysis.

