5.7. Protocol Deviations

Participants who experience events that may affect their PK profile (eg, lack of compliance with dosing) may be excluded from the PK analysis. At the discretion of the pharmacokineticist a concentration value may also be excluded if the deviation in sampling time is of sufficient concern or if the concentration is anomalous for any other reason.

A full list of protocol deviations will be compiled and reviewed to identify major and minor deviations prior to database closure.

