5.7.2. Deviations Assessed Post-Randomization

A full list of protocol deviations for the study report will be compiled prior to database closure. Any significant deviation from the protocol will be reviewed prior to database closure and a decision taken regarding evaluation for each analysis population.

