8.2. Statistical Analyses

Natural logarithm-transformed bosutinib AUC_{inf} , AUC_{last} and C_{max} will be analyzed using a mixed effect model with sequence, period and treatment as fixed effects and participant within sequence as a random effect. Estimates of the adjusted mean differences (Test- Reference) and corresponding 90% CIs will be obtained from the model.

The adjusted mean differences and 90% CIs for the differences will be exponentiated to provide estimates of the ratio of adjusted geometric means (Test/Reference) and 90% CIs for the ratios.

The following 2 comparisons will be performed:

- *Treatment A (Test) vs Treatment C (Reference);*
- *Treatment B (Test) vs Treatment C (Reference).*

The plasma PK parameters AUC_{inf} , C_{max} , AUC_{last} , T_{max} , CL/F , Vz/F and $t_{1/2}$ of bosutinib will be summarized descriptively by treatment. For AUC_{inf} , AUC_{last} and C_{max} , a listing of the individual participant ratios (Test-Reference) will be provided for the 2 comparisons described above. Individual participant PK parameters for AUC_{inf} , AUC_{last} and C_{max} will be plotted by treatment and overlaid with geometric mean. Concentrations will be listed and summarized descriptively by PK sampling time and treatment. Individual participant and median profiles of the concentration-time data will be plotted by treatment.

For summary statistics and median plots by sampling time, the nominal PK sampling time will be used, for individual participant plots by time, the actual PK sampling time will be used.

Residuals from the model will be examined for normality and the presence of outliers via visual inspection of plots of residuals vs predicted values and normal probability plots of residuals but these will not be included in the clinical study report. If there are major deviations from normality or outliers, then the effect of these on the conclusions will be investigated through alternative transformations and/or analyses excluding outliers. Justification for any alternative to the planned analysis will be given in the report of the study.

Table 3. PK Parameters to be Summarized Descriptively by Treatment

Parameter	Summary Statistics
AUC_{inf} , AUC_{last} , C_{max} , Vz/F , CL/F	N, arithmetic mean, median, cv%, standard deviation, minimum, maximum, geometric mean and geometric cv%.
T_{max}	N, median, minimum, maximum.
$t_{1/2}$	N, arithmetic mean, median, cv%, standard deviation, minimum, maximum.

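### Does the optional wording of the 2 x median Tmax vomiting rule leave the primary bioavailability ratios open to choice after the fact?

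*SAP*

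**What the plan says.** SAP 7.3 deals with vomiting in two consecutive sentences.

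- The first concerns a parameter whose estimate has a known cause of bias, with vomiting before absorption is finished as the example. Such a value is footnoted and "will not be included in the calculations of summary statistics or statistical analyses".
- The second reads: "Participants who vomit at or before 2 times of median T_{max} after drug administration may be excluded from PK analyses".

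Protocol 9.3.1 carries the same pair, and its second sentence ends "after drug administration may be excluded from PK analysis". Table 5 in that section gives the source of Tmax as "Observed directly from the data as time of first occurrence".

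Five other places bear on the point:

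- Protocol 9.3 promises that the SAP "will describe the analyses and procedures for accounting for missing, unused, and spurious data", and requires the SAP to be final before database lock and before any analysis.
- SAP 5.7 opens with "Participants who experience events that may affect their PK profile" and allows their exclusion. SAP 5.7.2 says that significant deviations "will be reviewed prior to database closure and a decision taken regarding evaluation for each analysis population".
- SAP 5.1.2 keeps in the parameter set anyone with a primary parameter from one period or more.
- SAP 8.2 says that the effect of outliers or non-normality "will be investigated through alternative transformations and/or analyses excluding outliers".
- SAP 4.1 and 4.2 state that there are no hypotheses and no decision rules.

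**The concern.** Taken alone, the second sentence leaves four things open.

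1. No criterion says when the option to exclude is used.
2. The unit is the participant, although in a three-period crossover a person who vomits once still supplies two sound profiles.
3. The median Tmax is not identified. It could be the historical 6 h in Protocol 2.2.1, this study's pooled median, or each treatment's own median.
4. No one is named to decide, and no date is set. A median from this study cannot exist until the samples have been assayed.

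On vomiting, the SAP repeats the protocol and adds nothing, despite what Protocol 9.3 promises. The event is also likely: Protocol 2.2.1 reports vomiting in 32.5% of 40 healthy participants given 500 mg with food. If exclusions could be chosen with the concentrations in view, the primary Test/Reference ratios could move. If whole participants were dropped, the 90% confidence intervals would widen more than they need to.

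**Working it through.** **Reading the two sentences together.** The first is mandatory and acts on the parameter. A profile that lost drug to vomiting is its own example, so it must come out whatever the second sentence allows. The second then marks the window in which vomiting raises the question. Because parameters are derived per period, and SAP 5.1.2 keeps a participant with one usable period, removing the affected period alone is the natural reading.

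**Window.** Twice a median Tmax at the nominal 4, 6 or 8 h sample is 8, 12 or 16 h. The historical 6 h gives 12 h. Over that assumed range, only vomiting between 8 and 16 h changes status with the choice of median.

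**Precision: inputs.** Protocol 9.5 gives 18 participants and within-participant SDs of 0.1675 (ln AUCinf) and 0.2499 (ln Cmax). The half-width is t(0.95, df) x SD x sqrt(2/n).

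**The plan's own figure.** Protocol 9.5 states ±0.1006 and ±0.1501. With n = 18 and participant as a fixed block, df = 54 - 18 - 4 = 32 and t = 1.694:

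- AUCinf: 1.694 x 0.1675 x sqrt(2/18) = 0.0946
- Cmax: 1.694 x 0.2499 x sqrt(2/18) = 0.1411

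The stated values are slightly wider; they match n = 16 with 29 df. They are not disputed here. The comparisons below use 0.0946 and 0.1411 so that one method runs throughout.

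**Number affected (assumed).** If 32.5% is a rate per participant over the whole study and all vomiting falls inside the window, 0.325 x 18 = 5.85, or about 6.

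**Half-widths.** Reduced-data rows are medians over 2000 random choices of vomiters and periods.

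| Case | AUCinf | Cmax |
|---|---|---|
| Full data | 0.0946 | 0.1411 |
| 6 vomit once, period dropped | 0.1052 | 0.1570 |
| 6 vomit twice, periods dropped | 0.1193 | 0.1779 |
| 6 vomit, participant dropped | 0.1192 | 0.1778 |
| 3 vomit once, period dropped | 0.0995 | 0.1484 |
| 3 vomit, participant dropped | 0.1046 | 0.1560 |

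Check on the participant-level row with a balanced n = 12: df = 20, t = 1.725, sqrt(2/12) = 0.4082, giving 0.1179 / 0.1760.

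For six vomiters with one period each, period-level exclusion widens the interval by 0.1052/0.0946 - 1 = 11%. At a true ratio of 1 the intervals become 0.900 to 1.111 (AUCinf) and 0.855 to 1.170 (Cmax), against 0.910 to 1.099 and 0.868 to 1.152 with full data. Dropping whole participants widens by 0.1192/0.0946 - 1 = 26%. If each vomits in two periods, the two rules give the same width.

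The SAP fits participant as random. With a between-participant SD assumed at 1.5 to 3 times the within-participant SD, the second row becomes 0.1046-0.1050 / 0.1561-0.1567, so the fixed-block figures serve.

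**Six of 18 is not an upper bound.** Protocol 2.2.1 does not say how many doses lie behind the 32.5%. If it were a rate per dose with independent doses, 1 - 0.675^3 = 69%, or about 12 of 18, would vomit at least once. Dropping whole participants would leave about 6: df = 8, t = 1.860, sqrt(2/6) = 0.5774, giving 0.180 / 0.268. Dropping periods would cost 0.325 x 54 = 17.6 of the 54 profiles.

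**The case for a change.** The strongest argument for a change is that the point estimate can move more than the interval widens. Suppose 4 of 18 Test profiles each lost half their exposure. Keeping them, compared with excluding them, multiplies the ratio by exp((4/18) x ln 0.5) = 0.86, with a range of 0.94 to 0.73 for losses of 25% to 75%. The safeguards are also partial. Footnotes disclose a choice but do not fix it beforehand. SAP 5.7.2 does not name vomiting, and it works to database closure, not to the release of concentrations. The outlier check in SAP 8.2 comes after results exist. Whether a participant counts as evaluable, and so may be replaced, hangs on the same judgement.

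Part of this stands. The median is undefined and the time of decision is unstated. But the example does not show that the optional sentence does harm. A profile that lost half its exposure to vomiting is a known biased estimate, and the mandatory sentence removes it. The option properly covers vomiting inside the window where absorption may already have been complete, and there keeping or dropping the profile should matter little. That exclusions would be settled after seeing concentrations is inferred from silence; nothing in either document plans it.

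A firmer rule has costs too. Compulsory exclusion at one common hour would discard sound late-window profiles. It would also apply one cut-off to intact capsules and to granules in soft food, which the documents give no basis for.

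**Conclusion.** The wording is loose, but no change to the plan follows. The 26% widening depends on dropping whole participants, which is the less natural reading. Under period-level exclusion the cost is about 11% in half-width for six single vomiters and about 5% for three (0.0995/0.0946). Much of that loss comes from the mandatory sentence in any case.

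These figures assume that the earlier 32.5% is a rate per participant, that all vomiting falls inside the window, and that the Protocol 9.5 SDs hold. Under a per-dose rate the loss of precision would be larger, but it would come mainly from the vomiting itself. The documents give neither the times of vomiting nor the exposure lost, so they determine neither the size nor the direction of any shift in the ratio, and no wrong result has been shown.

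The study is for estimation only, its exclusions are footnoted, and no pass/fail conclusion depends on them. Which median Tmax to use and when to settle the list are details that a pharmacokineticist and statistician can fill sensibly. Keeping the option instead of a fixed compulsory cut-off is a fair trade-off.

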8. STATISTICAL METHODOLOGY AND STATISTICAL ANALYSES

8.1. Statistical Methods

Precision of the estimate of PK parameters will be determined by constructing 90% confidence intervals around the estimated difference between the Test and Reference treatments using a mixed effects model based on natural log transformed data. The mixed effects model will be implemented using SAS Proc Mixed, with REML estimation method and Kenward-Roger degrees of freedom algorithm.

8.2. Statistical Analyses

Natural logarithm-transformed bosutinib AUC_{inf} , AUC_{last} and C_{max} will be analyzed using a mixed effect model with sequence, period and treatment as fixed effects and participant within sequence as a random effect. Estimates of the adjusted mean differences (Test- Reference) and corresponding 90% CIs will be obtained from the model.

The adjusted mean differences and 90% CIs for the differences will be exponentiated to provide estimates of the ratio of adjusted geometric means (Test/Reference) and 90% CIs for the ratios.

The following 2 comparisons will be performed:

- *Treatment A (Test) vs Treatment C (Reference);*
- *Treatment B (Test) vs Treatment C (Reference).*

The plasma PK parameters AUC_{inf} , C_{max} , AUC_{last} , T_{max} , CL/F , Vz/F and $t_{1/2}$ of bosutinib will be summarized descriptively by treatment. For AUC_{inf} , AUC_{last} and C_{max} , a listing of the individual participant ratios (Test-Reference) will be provided for the 2 comparisons described above. Individual participant PK parameters for AUC_{inf} , AUC_{last} and C_{max} will be plotted by treatment and overlaid with geometric mean. Concentrations will be listed and summarized descriptively by PK sampling time and treatment. Individual participant and median profiles of the concentration-time data will be plotted by treatment.

For summary statistics and median plots by sampling time, the nominal PK sampling time will be used, for individual participant plots by time, the actual PK sampling time will be used.

Residuals from the model will be examined for normality and the presence of outliers via visual inspection of plots of residuals vs predicted values and normal probability plots of residuals but these will not be included in the clinical study report. If there are major deviations from normality or outliers, then the effect of these on the conclusions will be investigated through alternative transformations and/or analyses excluding outliers. Justification for any alternative to the planned analysis will be given in the report of the study.

Table 3. PK Parameters to be Summarized Descriptively by Treatment

Parameter	Summary Statistics
AUC_{inf} , AUC_{last} , C_{max} , Vz/F , CL/F	N, arithmetic mean, median, cv%, standard deviation, minimum, maximum, geometric mean and geometric cv%.
T_{max}	N, median, minimum, maximum.
$t_{1/2}$	N, arithmetic mean, median, cv%, standard deviation, minimum, maximum.

For AUC_{inf} , AUC_{last} and C_{max} a listing of the individual subject ratios (Test/Reference) will be provided. Box and whisker plots for individual subject parameters (AUC_{inf} , AUC_{last} and C_{max}) will be presented by treatment and overlaid with geometric means.

Supporting data from the estimation of $t_{1/2}$ and AUC_{inf} will be listed by treatment and analyte: terminal phase rate constant (k_{el}); goodness of fit statistic from the log-linear regression (r^2); the percent of AUC_{inf} based on extrapolation ($AUC_{extrap\%}$); and the first, last, and number of time points used in the estimation of k_{el} . This data may be included in the clinical study report.

Presentations for *bosutinib (PF-05208763)* concentrations will include:

- A listing of all concentrations sorted by subject ID, treatment and nominal time postdose. The concentration listing will also include the actual times. Deviations from the nominal time will be given in a separate listing.

- A summary of concentrations by treatment and nominal time postdose, where the set of statistics will include n, mean, median, standard deviation, coefficient of variation (cv), minimum, maximum and the number of concentrations above the lower limit of quantification.
- Median concentrations time plots (on both linear and semi-log scales) against nominal time postdose by treatment (all treatments on the same plot per scale, based on the summary of concentrations by treatment and time postdose).
- Mean concentrations time plots (on both linear and semi-log scales) against nominal time postdose by treatment (all treatments on the same plot per scale, based on the summary of concentrations by treatment and time postdose).
- Individual concentration time plots by treatment (on both linear and semi-log scales) against actual time postdose (there will be separate spaghetti plots for each treatment per scale).
- Individual concentration time plots by subject (on both linear and semi-log scales) against actual time postdose [there will be separate plots for each subject (containing all treatments) per scale].

For summary statistics, median and mean plots by sampling time, the nominal PK sampling time will be used, for individual subject plots by time, the actual PK sampling time will be used.

8.3. Safety Analysis

All participants assigned to investigational product and who take at least 1 dose of investigational product. Participants will be analyzed according to the product they actually received.

8.3.1. Treatment and Disposition of Participants

Data will be reported in accordance with the sponsor reporting standards.

8.3.2. Demographic and Clinical Examination Data

A breakdown of demographic data will be provided for age, race, weight, body mass index, and height. Each will be summarized by sex at birth and 'All Participants' in accordance with the sponsor reporting standards.

8.3.3. Discontinuation(s)

Participant discontinuations and temporary discontinuations due to adverse events will be detailed and summarized by treatment.

Data will be reported in accordance with the sponsor reporting standards.

